### **3. Family Management**

There are a number of parenting practices (e.g., limit-setting, problem-solving, coercive processes, reinforcement), but studies suggest that these dimensions of parenting are highly correlated (Dishion et al., 1998). Consequently, we will focus on monitoring and communication with measures completed by both teens and their parents.

Parent Monitoring Questionnaire (PMQ). The PMQ (Kerr & Stattin, 2000) is a 24 item youth and parent report measure designed to assess parental monitoring and sources of parental knowledge (child disclosure, parental solicitation, parental control). The monitoring subscale has demonstrated good reliability ( $\alpha = .82$  for parents;  $\alpha = .85$ ,  $r_{tt} = .83$  for child) and correlates with adolescent internalizing and externalizing maladjustment, deviant peer relationships, and family discord (Kerr & Stattin, 2000).

Parent Reactions to Youth AOD Use. Parents and teens will complete an 8-item questionnaire, adapted from Chassin et al. (1998a) to be inclusive of alcohol or drug use, about the likelihood of parents using various parent strategies to deal with children's AOD use.

Parent-Adolescent General Communication Scale. This is a youth and parent report measure that assesses the positive and negative aspects of general parent-adolescent communication and the content and process of parent-teen interactions. Internal consistency of the two subscales, Open Family Communication and Problems in Family Communication, ranges from .77 to .88 (Barnes & Olson, 1982).

Parent-Adolescent Alcohol and Drug Communication Scale. This scale is an adapted version of the PASCS described above, and assesses the process and content of alcohol and other drug use communication between parents and teens.

Parent-Adolescent Sexual Communication Scale (PASCS). The PASCS is a youth and parent report measure that assesses the process and content of sexual communication between parents and teens (e.g., when to start having sex). Internal consistencies range from .65 to .86 (Dutra et al., 1999; Miller et al. 1998).

Conflict Behavior Questionnaire (CBQ). The CBQ (Robin & Foster, 1989; Prinz, Foster, Kent, & O'Leary, 1979) measures perceived conflict and negative communication in the family in the two to three weeks preceding the assessment session. Parallel forms are completed by the adolescent and the parent. In two parent families, the adolescent completes two CBQ's, one with reference to each parent. Each form yields an appraisal of the other, and an appraisal of the relationship between the respondent and the other.

FAsTask Video Code. The FAsTask (described previously) provides an in vivo assessment of parenting behaviors and parent-child relationships. We limited the video assessment to 3 tasks (Problem-solving truancy, substance use norms and risk behavior norms) because these are the primary outcomes examined in this application. We also tried to limit reactive effects by limiting the number of tasks. The first follow-up is 3 months after the baseline assessment, so any reactive effects are likely to be small.

### **4. Other Problem Behaviors**

Child Behavior Checklist. See description under Screening Measures (above).

Reckless Behavior Questionnaire (Shaw et al., 1992) is 10 items that assess how often the adolescent engaged in a variety of risk-taking behaviors and selected items from the Adolescent Health Behavior Questionnaire (Jessor et al., 1980) will be used to assess risky sexual behavior.

School Attendance TLFB. Incidences of cutting classes and skipping school will be assessed at each contact point using the Timeline Follow-back Interview (TLFB; Sobell et al., 1980; Sobell & Sobell, 1992, 1996). The procedures for collecting information regarding school truancy will be similar to the ones used on the TLFB for substance use. These procedures will not only allow us to collect data on school truancy but will also allow us to examine the co-occurrence of SU and school truancy. Similar to the TLFB for substance use, information will be collected for the last 90 days at baseline, 3-month, and 6-month follow-ups.

Truancy and Academic Performance. With permission from both school personnel and parents, data on truant behavior and grade point average will also be obtained for each student from school records provided by the school office personnel. These procedures have been successfully implemented in previous school-based studies examining school performance (Zimmerman et al., 2002).

### **5. Peer Influences**

Peer Substance Use and Peer Tolerance of Substance Use (Chassin et al., 1993, 1996). Using items adapted from The Monitoring the Future Study, children estimate how many of their friends used alcohol, marijuana, and other drugs occasionally and regularly. They also indicate how their close friends would feel about their use of these drugs. Chassin et al. (1996) report high coefficient alphas (.89 - .93) for both measures. Because the two scales are highly correlated ( $r = .59 - .63$ ), a mean composite score is calculated.

Parental Management of Peers Inventory (PMPI; Mounts, 2002) is a 25-item child-report measure of how much the child perceives their parents to be involved in their peer relationships. Four factors summarize the valence of friendship choice and encouragement of friendships (Mounts, 2002).

Parent's Beliefs and Peers and Child Peer/Social Skills measures degree of deviant and prosocial peers (Dishion & Kavanagh, 2003). Separate scores will be derived for parents and adolescent. Deviant peers is the percentage of friends involved in problem behavior and drug use. Both parent and adolescent measures have demonstrated reliabilities within the acceptable range: Cronbach's alpha for parent reports = .75, for adolescent report .67 (Stormshak, Comeau & Shepard, 2004).

## **6. Teen Attitudes Toward AOD Use**

Marijuana Effect Expectancy Questionnaire (MEEQ). The MEEQ (Schafer & Brown, 1991) is a 48-item child self-report measure that assesses both positive and negative expectations associated with use of marijuana. Six scales are derived – Cognitive & Behavioral Impairment, Relaxation & Tension Reduction, Social & Sexual Facilitation, Perceptual & Cognitive Enhancement, Global Negative Effects, and Craving & Physical Effects. The MEEQ has been validated in children as young as age 12 (Aarons et al., 2001). The MEEQ demonstrates adequate internal consistency (Kuder-Richardson-20 coefficients from 0.82-0.66). The MEEQ, as compared with the well-established adolescent version of the Alcohol Expectancy Questionnaire (AEQ-A, Christiansen et al., 1982), demonstrated convergent validity with AEQ-A scales of like content ( $r's=.25-.43$ ) and divergent validity with AEQ-A scales of contrasting content ( $r=-.36$ ).

Brief Situational Confidence Questionnaire (BSCQ). The BSCQ is a modified version (Sobell, 1996) of the original 100-item Situational Confidence Questionnaire (SCQ; Annis, 1986) which was designed to tap eight self-efficacy situations clients report as being precipitants to relapse. The eight items are derived from Marlatt's relapse prevention model (Marlatt & Gordon, 1985) and correspond to the subscales defined by Annis and Davis (1988) for the SCQ-100. These subscales are include negative emotional states, negative physical states, positive emotional states, interpersonal conflict, social problems, and, positive emotional states. Responses are provided on 10-point Likert scales (i.e., 10% increments, from 0% = not at all confident to 100% = completely confident). The Cronbach's alpha coefficient was 0.85 in one study (Breslin et al., 2000).

This measure will be used to examine changes in adolescents' confidence levels as a result of the intervention.

Motivation to Abstain and Perceived Difficulty of Abstaining from Marijuana. Adolescents will respond to items asking "How motivated are you to abstain from marijuana use in the next 30 days?" and "How difficult will it be for you to abstain from marijuana for the next 30 days?" on a 10-point scale. Single-item measures of readiness and motivation to change substance use behavior have demonstrated satisfactory validity in adult samples (Amodei & Lamb, 2004; Miller & Johnson, 2008) and in adolescent samples (King et al., 2009).

Youth Alcohol and Drug Survey (Werch, 1996) is a child self-report measure that has subscales which assess SU-related cognitive, social, behavioral, and environmental risk and protective factors. Perceived susceptibility and severity of alcohol-related consequences (alpha coefficients = .84 and .90), benefits of avoiding alcohol (alpha = .84), motivation to avoid alcohol (alpha = .93), intention to use alcohol (alpha = .82), and cues to avoid alcohol (alpha = .89; Werch et al., 1997) will be used in data analysis.

## **7. Substance Abuse and Mental Health Treatment Contacts**

Additional substance abuse and mental health services that families obtain will be counted and reviewed at each of the follow-up points using the Child and Adolescent Services Assessment (CASA). The CASA (Burns et al., 1997) is a semi-structured interview that obtains information about service use for substance and mental health problems across multiple sectors (e.g., juvenile justice, schools). Adequate reliability has been demonstrated for this measure (ICCs=.74-.76) (Farmer et al., 1994).

## **8. Intervention Acceptability**

Exit interviews. An "exit interview" will be completed with parent(s) in the experimental condition specifically about the FCU. In addition, the parent report forms on FCU session content used to track treatment fidelity and competence also provide valuable feedback regarding the intervention. Adolescents will also be interviewed regarding the IMI. Similarly, treatment providers will also be interviewed regarding acceptability of the intervention to each client as well as themselves.

Session Evaluation Form (SEF; Harper et al., 2003). The SEF is a brief 13-item questionnaire that will be given to participants at the end of the IMI and FCU. This questionnaire consists of 10 items on a 4-point response scale about the participant's experience (i.e., was it interesting, was it relevant to their life, etc). Three open-ended items query participants about what was most and least useful about the interventions.

## **5e. Data Analysis Plan**

First, all forms will be checked for any missing data following interviews and prior to data entry. All data will be entered into the project computer twice using double entry. Back-up copies of data will be made on a regular basis, and copies of data will be kept on a server to avoid accidental loss. Attrition effects will be evaluated by testing whether systematic differences exist between those participants who complete the research versus those who drop out. We will initially inspect distributions for outliers and deviations from normality and will perform the necessary modifications to adjust for these issues. We will also examine any pre-existing differences between the two conditions in demographic composition and all measures collected at baseline. Pre-existing group differences in these variables will be controlled in subsequent analyses, using baseline scores as covariates. While both parents can participate in the intervention, we will use the assessment of the primary caretaker in all data analyses. On outcomes such as parental monitoring we expect to find discrepancies between child and parent report; thus, all analyses will be conducted separately for parent and child. With data from only 80 subjects (40 per group) in intent-to-treat analyses, our primary emphasis will be on calculating effect sizes for between group differences.

Sample representativeness and data imputation. Following Little and Rubin (1987) and Diggle and Kenward (1994), we distinguish between completely random drop-outs (independent of phenotype or covariate, MCAR), random drop-out (drop-out may depend upon past measures, but is not dependent on what the measure would have been at the time of missed assessment, MAR) and informative drop-out (may depend on prior variables and on state at possible time of missed assignment). We are concerned with informative drop out. If necessary, standard methods of multiple imputation (Little, 2002; Schafer, 1997) will be used for variables where unplanned missingness is an issue. For each time point, we will conduct analyses to identify systematic biases that may have arisen through non-participation (non-random dropout).

**Aim 1.** Treatment manual development does not require statistical analyses. The research team will meet with the PI at the beginning of the project, at the end of the open trial and end of the RCT to review the manual and suggest adaptations. With regard to feasibility, the following information will be calculated: refusal and enrollment rates, average number of days to intervention completion, and withdrawal rates of enrolled families. Acceptability will be examined by calculating percentage of "agree" or "strongly agree" answers on the SEF, with 80% set as an acceptable criterion. Treatment provider ratings conducted at post-intervention will also be calculated to determine clinician acceptability. Open-ended question responses at post-intervention and at completion of the follow-up assessment will also be qualitatively reviewed.

**Aims 2 - 4.** The domains to be analyzed, outlined in Table 2, include substance use (Aim 2), other problems (school, risky sexual behavior, Aim 3), and potential mediating processes including family management (Aim 4a), peer influences (Aim 4b) and teen cognitions (Aim 4c). The basic analytic strategy entails latent growth modeling to assess change in outcomes over time. This model allows for the inclusion of both categorical and continuous independent variables and for appropriate modeling of covariance structures when observations are correlated over time. Each teen and family outcome will be entered as a dependent variable in separate analyses with intervention condition serving as the primary independent variable. Appropriate time invariant covariates (e.g., age, sex, etc.) will be included as determined by preliminary analyses described above. Substance use in general, and marijuana use in particular, at baseline will be co-varied in one analysis to determine if there are any differential effects of the interventions by prior substance use. Post-hoc power analyses will be conducted using the beta weight and standard error of the estimate for intervention group to determine the number of subjects necessary for the given differences in outcomes to be significant in future studies. Measures of association (adjusted mean differences) and 95% confidence intervals will also be calculated to assess the effect size of the IMI/FCU.

The basic analytic strategy described above is limited by the small sample size of this treatment development study. Although the investigation of all outcomes using latent growth modeling will lay the groundwork for a future R01 trial, additional analyses will be helpful to provide more information about effect sizes. An estimate of the intervention effect sizes at each assessment with appropriate covariates, as well as the correlation between the same dependent variable at adjacent assessments, will be conducted. These parameters will be used to determine necessary sample sizes for a future clinical trial by conducting power analyses for repeated measures designs.

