**5B1. Procedure.** Parent(s) or legal guardian(s) (hereafter referred to as "parents") of adolescents in the targeted age range will be recruited from the RI Truancy Court Program (see letters of support). Following arraignment procedures, families will be given information about the project by study staff who will be present at all truancy court arraignments and who will also answer any questions parents may have. Interested participants will be contacted by study staff at their second Truancy Court arraignment appointment. During this meeting, they will receive an oral and written description of the study, including a description of the project procedures, number of appointments and compensation for participation, potential risks and benefits, and confidentiality. Families who provide parental consent and adolescent assent will be administered the screening battery. If the child does not meet the substance use and CBCL inclusion criteria, they will be given a package of educational materials regarding truancy and SU.

**Assignment of participants to conditions.** In the open trial portion, the first 20 families will receive the IMI/FCU in order to inform adaptations to the current protocol and to examine its feasibility and acceptance. After this open trial, 100 families will be recruited and randomized into either the experimental or the comparison control condition. These assignments will be made soon after completing the baseline assessment and through random assignment using the urn method (Stout et al., 1994). Urn randomization assigns participants in a given subgroup to intervention conditions, but systematically biases the randomization in favor of balance among the intervention conditions. Participants will be randomized according to gender, substance abuse (yes or no), and meeting CBCL cut-off for internalizing only versus externalizing only or externalizing/internalizing.

**5B2. Baseline and follow-up assessments (IMI/FCU and PE).** Parents and teens will complete the

assessment battery described below at their local school. In person follow-up assessments will be held at 3 and 6 months following the baseline assessment. An RA who will be blind to condition assignment will conduct each follow-up assessment. The follow-up assessment battery will be identical to baseline.

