Drug Use Questionnaire. This measure used in both MI grants assesses the number of days in the past 30 days teens used nicotine, marijuana, cocaine, LSD, PCP, inhalants, etc. Internal consistency in our sample was .75 (alpha = .80 when inhalants was dropped). Test/retest for mean number of days each substance was used was .83 from 3 to 6 month follow-up and .94 from 6 to 12 month follow-up.

Parent Substance Use. Parents will report on the extent to which they use alcohol, marijuana, and other drugs, and if they report no current use of a substance, whether they have stopped using the substance because they had a problem with use of the substance in the past. This information will be used for feedback purposes during the FCU.

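### Covariates are picked by observed baseline differences between randomized arms, so the per-assessment effect sizes need not adjust for the outcome's own baseline and no analysis must include all three urn factors

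*Combined protocol and SAP*

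**What the plan says.** The opening paragraph of 5e has the two conditions compared on demographics and on every baseline measure. It continues: "Pre-existing group differences in these variables will be controlled in subsequent analyses, using baseline scores as covariates". No test or threshold is given.

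Under Aims 2 - 4, the latent growth models take their covariates from that comparison: "Appropriate time invariant covariates (e.g., age, sex, etc.) will be included as determined by preliminary analyses described above". One covariate is named in advance, but for a single analysis aimed at differential effects: "Substance use in general, and marijuana use in particular, at baseline will be co-varied in one analysis".

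The last paragraph of 5e adds supplementary estimates: "An estimate of the intervention effect sizes at each assessment with appropriate covariates". Their covariates are not listed. A second quantity is to be estimated alongside them: "as well as the correlation between the same dependent variable at adjacent assessments". The purpose of both is stated: "These parameters will be used to determine necessary sample sizes for a future clinical trial by conducting power analyses for repeated measures designs". Aims 2 - 4 gives a second sizing route, a post-hoc power analysis from the growth model's intervention coefficient and its standard error.

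The urn factors are in 5B1, under assignment to conditions: "Participants will be randomized according to gender, substance abuse (yes or no), and meeting CBCL cut-off for internalizing only versus externalizing only" or both. Section 5e never mentions them.

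**The concern.** In a randomized trial, a baseline difference between arms shows how the allocation happened to fall. It does not show that a variable predicts outcome, and prediction is what makes adjustment worthwhile. A rule triggered by imbalance therefore tends to bring in variables that do not help and to leave out those that do. The outcome's own baseline is usually the strongest predictor, yet it enters only when it happens to be imbalanced. The urn factors are the least likely to enter, because the urn pushes them towards balance.

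Precision is at stake. Section 5e makes between-group effect sizes the primary emphasis with 80 analysed, and the per-assessment effect sizes feed the sizing of the next trial. The covariate set also stays open until the arms have been compared.

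**Working it through.** **Plan's own figure.** Table 3 gives power .60 at d = .50 with 40 per group. An unadjusted two-sided t test at 5% gives .598, and 63 per group for 80% power, as the plan states. The planned power therefore takes no credit for covariates.

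**What an imbalance trigger selects (p < .05 assumed).** Table 2 lists 4 + 7 + 5 + 4 + 4 + 1 = 25 non-background measures given to both arms at baseline. By chance, 25 × .05 = 1.25 would be selected. This counts instruments; subscales, parent and adolescent forms and demographics would raise it. In simulation an outcome's own baseline was selected in about 5% of trials, and each urn factor in about 1%.

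**Interval width by formula.** Work in SD units with 40 per arm, so 2/40 = .05. Rho is the correlation of baseline with follow-up.
- Unadjusted: 2 × t(78) × √.05 = 2 × 1.991 × .2236 = .890.
- Baseline plus three urn factors, urn factors not prognostic: 2 × t(74) × √[.05 × (77/73) × (1 − rho²)] = .915 × √(1 − rho²). The factor 77/73 is the average cost of four covariates.
- Break-even: rho² = 1 − (.890/.915)², so rho is about .23.

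**Simulation.** 20,000 trials per rho; urn on three factors, 100 randomized, 20 dropped at random, d = .50. The selected rule stays near the unadjusted width because it seldom selects the useful covariate.

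| rho | Width, selected | Width, fixed (simulated) | Width, fixed (formula) | Power, selected vs fixed |
|---|---|---|---|---|
| 0 | .892 | .907 | .915 | .590 vs .575 |
| .2 | .891 | .889 | .897 | .592 vs .595 |
| .3 | .890 | .864 | .873 | .595 vs .620 |
| .5 | .887 | .785 | .793 | .594 vs .699 |
| .7 | .879 | .648 | .654 | .610 vs .856 |

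Coverage was .949 to .971 for the selected rule over rho 0 to .83, so its intervals are, if anything, too wide.

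**Which rho applies.** No baseline-to-follow-up value is given. The nearest is for days of drug use in an earlier sample: "Test/retest for mean number of days each substance was used was .83 from 3 to 6 month follow-up". It is an upper guide, since it lies between two follow-ups and the entry rule (6 or more uses in 90 days) truncates baseline use. If 30% to 70% of screened teens qualify (assumed, bivariate normal), .83 falls to .61-.72, .5 to .29-.38 and .3 to .16-.22. At .72 the fixed width is .915 × √(1 − .518) = .635, which against .88 is a 28% reduction. At .16-.22 there is no gain. Parental monitoring is not truncated by this rule.

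**What the urn factors add.** Take rho = .5 and each urn factor correlated .2 with outcome, the three mutually uncorrelated. Baseline alone gives 2 × t(77) × √[.05 × (77/76) × .75] = .776. With all four, R² = 3 × .2² + (.5 − 3 × .2 × c)² / (1 − 3c²), where c is each factor's correlation with baseline.
- c = 0: R² = .37, width .915 × √.63 = .73 (simulated .72).
- c = .2: R² = .284, width .77.
- c = .4: R² = .25, width .79, no gain over baseline alone.

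If the urn factors are not prognostic, adding them to baseline widens the interval by about 1% (.776 to .785). In the growth model, adding them ran from 2% wider to 7% narrower over the settings tried, the narrower end with the factors correlated .2 with change.

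**Binary outcomes (75% vs 52%, h about .48).** SD of h, unadjusted versus covariate-standardized: .226 vs .227 at r = .3, .229 vs .215 at .5, .228 vs .197 at .7. Mean h was −.49 both ways. An adjusted log odds ratio moved from −1.04 to −1.33 at r = .5, because it estimates a different quantity.

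**Next-trial size, n = 63 × (.5/d)², at d = .50 ± one SD of the estimate.** At rho .5 (SD .216 vs .198): 31-195 vs 32-173 per group. At rho .7 (SD .207 vs .162): 32-184 vs 36-138. This ignores the repeated-measures correlation.

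**The case against.** The strongest reply is that baseline is already used where it matters most. The basic strategy is latent growth modelling, in which baseline is an occasion, and its coefficient and standard error give a sizing route that carries baseline information. This stands: the large contrasts above apply only to the supplementary effect sizes, and the growth model lacks only the urn factors. A reader might infer that the next trial's size rests wholly on estimates that ignore baseline. The documents do not support that, and even the supplementary route uses the correlation between adjacent assessments.

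Second, an outcome's baseline could well be meant as an appropriate covariate. That is possible, but 5e ties adjustment to observed group differences and lists nothing, so baseline is neither excluded nor guaranteed.

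Third, rho is unknown and the urn factors may add nothing. Both points stand. The urn-factor gain depends on assumed correlations and vanishes if those factors overlap enough with the baseline score. The firmer reason to include them is that they are the randomization factors.

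Fourth, this is a treatment-development trial. The plan itself acknowledges that effect sizes from small samples are unstable, and the next-trial ranges stay wide under either rule. That tempers the priority, but does not justify giving up precision that needs only a change of wording.

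**Conclusion.** The concern holds as a loss of precision. A reader might infer bias or an inflated Type I error from choosing covariates after seeing the arms. The documents do not support that: the rule turns on baseline differences, and under the assumed p < .05 trigger with baseline as the candidate covariate, simulated Type I error was .048 at rho .3 and .028 at rho .83, which is conservative.

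The size depends on rho: little at .3, about a tenth of the interval width at .5, about a quarter at .7, and a slight loss below about .2. These figures assume a continuous outcome, d = .50, 80 analysed after random dropout, a p < .05 trigger that the plan does not state, and urn factors that are not prognostic. The change should be made because effect sizes are this trial's main product, with medium confidence in how much it gains.

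**What to change.** In 5e, state that each 3- and 6-month effect size adjusts, whatever the observed balance, for:
1. the baseline value of that outcome or, where the entry rule makes it constant or none exists, a named related baseline measure (for example Timeline Follow-Back use days for any use and for latency to first use);
2. the three urn factors: gender; substance abuse yes/no; CBCL internalizing only versus externalizing only or both.

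Include the urn factors in the growth models. For binary outcomes, report a covariate-standardized difference in proportions, or h from the standardized proportions, rather than an adjusted odds ratio. List any other covariate, such as age, by expected prognostic value before the arms are compared. Keep baseline comparisons as description.

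The cost is wording, since every variable is already collected at screening or baseline. The per-assessment models use up to four degrees of freedom; the growth models need more parameters if the factors enter both intercept and slope. If none of the covariates is prognostic, power falls by about 1 to 1.5 points (.590 to .575 in the simulation).
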